17.1.1 ALL TEAEs

Incidence of TEAEs will be presented by System Organ Class (SOC) and Preferred Term (PT) and also broken down further by maximum intensity, and by relationship to study medication.

An overview of AE's will be provided with patients experiencing n (%) at least one SAEs, AEs, TEAE, treatment related TEAE, treatment related SAE, Number of patients died and patients discontinuing the study due to AE.

An overview of AE summary will be provided each period wise separately.

17.1.2 INTENSITY

Intensity is classed as mild, moderate, severe. TEAEs starting after the first dose of study medication with a missing intensity will be classified as severe. If a subject reports a TEAE more than once within that SOC/PT, the AE with the greatest intensity will be used in the corresponding intensity summaries.

17.1.3 RELATIONSHIP TO STUDY DRUG

Relationship, as indicated by the Investigator, is classed as “ Probable”, “Possible”, “Unlikely” , “Not related” and “Unknown”. A “related” TEAE is defined as a TEAE with a relationship to study medication as ” Probable”, “Possible” and “Unknown” to study medication. TEAEs with a missing/Unknown relationship to study medication will be regarded as “*probable*” to study medication. The rest of the AEs will be considered as not related (“Unlikely” and “Not related”).

If a subject reports the same AE more than once within that SOC/PT, the AE with the worst case relationship to study medication will be used in the corresponding relationship summaries.

Document:	\\ieedc-vnasc01\BIOSdata\Newron\Sarizotan\PXA76395\Biostatistics\Documentation\SAP		
Author:	[name]	Version Number:	V2
		Version Date:	[30March2020]
Template No:	CS_TP_BS016 – Revision 4	Reference:	CS_WI_BS005
Effective Date:	01Apr2016		

17.1.4 AEs LEADING TO PATIENT DISCONTINUATION

AEs leading to permanent discontinuation of patient will be identified.

For AEs leading to discontinuation of patient, summaries of incidence rates (count and percentages) by SOC and PT will be prepared.

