Amend. 1, 19Jan2016; Amend. 2, 18May2016; Amend. 3, 21Oct2016; Amend. 4, 03Mar2017; Amend. 5, 29Mar2017; Amend. 6, 13Apr2017; Amend. 7, 02Oct2017; Amend. 8, 02Nov2017; Amend. 9, 11Feb2018; Amend. 10, 29Nov2018; Amend. 13, 10Dec2019; Amendment 14, 17 March 2020, Clean, Final

In the initial double-blind period, the study medication will be administered as capsules of 2, 5 and 10 mg dosage strengths of sarizotan, or an equal number of matching placebo capsules. Doses will be administered as 1 capsule *bid* given at approximately 8:00 AM and 8:00 PM, with an interval of approximately 12 hours (minimally 6 hours) between doses.

If intolerance develops, the Investigator may reduce a patient's dose to the next lower level at any time. If patients do not tolerate the proposed titration and target dose, the investigator will instruct the caregiver to administer only one of the two daily doses (e.g. 2 or 5 mg once daily) for a few days prior to reinitiating the intended *bid* dose (e.g. 2 or 5 mg *bid*). If the dose is still not tolerated, a reduction to a lower rescue dose will be permitted. Patients unable to tolerate Dose Level 1, even after a dose interruption, should be discontinued from the study. Dose titration should be completed by Day 14, after which patients will continue on their maximum tolerated dose (MTD) through the final dose in the double-blind period, unless intolerance develops and a dose reduction is warranted.

In the open-label extension treatment period, all patients, including those originally randomized to placebo, will receive treatment with sarizotan, and will start at a dose of 2 mg *bid* (patients 4 to <13 years of age and weighing 10 to <18 kg, and patients \geq 13 years of age but weighing <25 kg) or 5 mg *bid* (patients \geq 13 years of age and weighing \geq 25 kg). The first dose (2 or 5 mg) will be administered in the clinic (if the morning dose was given, wait at least 6 hours after the prior dose before administration), in the presence of a licensed physician, on the same day as the Week 24 evaluations from the initial period, if possible. The date, time, and number of capsules administered in the hospital setting on the first day of open-label dosing will be recorded on the CRF. If no tolerability issues are noted in the 4-hr post-dose follow-up period, the patient will then receive a supply of study medication (sarizotan 2-mg or 5-mg capsules) for the 4-week period until the next scheduled visit and return home.

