 - the subject's clinical state, or
 - other therapy administered, or
 - a diagnostic/interventional procedure.

3. **Unlikely**
 - a) The adverse event follows a reasonable temporal sequence from administration of the study agent;
 - b) Other reasons are more likely to be the cause of the adverse event, based on the present knowledge of the
 - disease under treatment, or
 - other therapy administered, or
 - study drug;
 - c) A causal relationship between the adverse event and the study drug can't be ruled out with certainty.

4. **Not Related** The event is either a pre-dose event or is definitely due to causes separate from the administration of the study agent, i.e.,
 - documented pre-existing condition
 - technical and manual procedural problems
 - concomitant medication
 - subject's clinical state.

5. **Unknown** The event does not meet any of the above criteria because of:
 - conflicting data and/or
 - dubious or insufficient/poor evidence
 - the event is not judged as related or not related.

Action Taken in Relation to the Adverse Event:

1. **None**
2. **Drug treatment required** (a medication was prescribed or changed; record on the Concomitant Medication section of the Case Report Form)
3. **Change in dose of concomitant medication**
4. **Non-drug treatment required** (a non-drug treatment was prescribed or changed, record under “Comments” in the Adverse Event section of the Case Report Form)
5. **Hospitalization or prolonged hospitalization**
6. **Diagnostic or clinical test(s) conducted** (attach a copy of the results to the Case Report Form)
7. **Subject discontinued from the study**

Action Taken with the Study Medication:

1. **Study medication dose interruption**
2. **Study medication dose reduction**
3. **Study medication discontinuation**
4. **None**

Subject Outcome:

1. **Recovered without sequelae**
2. **Recovered with sequelae** (describe the sequelae under “Comments” in the Adverse Event section of the Case Report Form)
3. **Not Recovered, event on-going** (follow the subject until a definite outcome can be determined. When follow-up data are collected, report follow-up information under “Comments” in the Adverse Event section of the Case Report Form; if event is serious, fill in a follow-up Serious Adverse Event Report)

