17.1. ADVERSE EVENTS

Adverse Events (AEs) are be coded using MedDRA central coding dictionary version 22.0.

An AE is defined as any untoward medical occurrence in a patient or clinical investigation patient administered a pharmaceutical product that does not necessarily have a causal relationship with the product. An AE can therefore be any unfavorable and unintended sign (including a new, clinically important abnormal laboratory finding), symptom, or disease, temporally associated with drug administration, whether or not related to the product.

The above definition covers also cases of

- Exacerbation of pre-existing diseases or conditions.
- Pre-existing diseases or conditions (reported at time of screening in medical history) will not be considered AEs unless there is an increase in the frequency or severity, or a change in the quality of the disease or condition.
- Events occurring in subjects treated with matching placebo are also considered AEs.

An AE will be defined as a treatment-emergent adverse event (TEAE) if the first onset (or

Document:	\\ieedc-vnasc01\BIOSdata\Newron\Sarizotan\PXA76395\Biostatistics\Documentation\SAP		
Author:	[name]	Version Number:	V2
		Version Date:	[30March2020]

Template No: CS_TP_BS016 – Revision 4
 Effective Date: 01Apr2016

Reference: CS_WI_BS005

worsening, in the case of pre-existing disease) is after the first administration of study treatment throughout the study. In addition, any serious adverse events (SAEs) reported in the 30 days following last dose of IMP will be recorded and counted in the final clinical study report.

See [Appendix 1](#) for handling of partial dates for AEs. In the case where it is not possible to define an AE as treatment emergent or not, the AE will be classified by the worst case; i.e. treatment emergent.

An overall summary of number of subjects within each of the categories described in the subsection below, will be provided as specified in the templates. Listings will include TEAEs and Non-TEAEs. Listings will be provided for TEAEs, SAE and TEAEs leading to discontinuation from study for safety analysis set.

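### The SAP names no by-arm summary of adverse events that led to dose reduction or interruption, although the protocol records that action for every event

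*SAP*

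**What the plan says.** **Protocol, handling of intolerance.** Section 10.2 states: "If intolerance develops, the Investigator may reduce a patient's dose to the next lower level at any time". It also lets the caregiver give one of the two daily doses for a few days before the twice-daily dose is resumed, with a lower dose permitted if that fails. Discontinuation is named there for patients who cannot tolerate Dose Level 1 even after an interruption. After titration, patients stay on their maximum tolerated dose.

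**Protocol, data collected.** Section 13.1.2 requires the action taken with study medication to be recorded for each adverse event. The options include "Study medication dose interruption" and "Study medication dose reduction", alongside discontinuation and none.

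**Protocol, analysis.** Section 15.2.3 promises a report of how many subjects were on each dose level and how many capsules they took. Section 15.2.5 compares sarizotan and placebo on SAEs, adverse dropouts, TEAEs and clinically significant abnormalities.

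**SAP.** The overview in 17.1.1 covers SAEs, AEs and TEAEs and ends with "treatment related TEAE, treatment related SAE, Number of patients died and patients discontinuing the study due to AE". The same section adds: "Incidence of TEAEs will be presented by System Organ Class (SOC) and Preferred Term (PT) and also broken down further by maximum intensity", and a breakdown by relationship. Section 17.1.4 says "AEs leading to permanent discontinuation of patient will be identified" and summarises those events by SOC and PT. Section 17.1 states: "Listings will be provided for TEAEs, SAE and TEAEs leading to discontinuation from study for safety analysis set". Section 13 defines exposure as last dose date minus first dose date plus one, disregarding interruptions and compliance. Section 3.3 declares no changes from the protocol.

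**The concern.** Tolerability is a stated objective, and the design titrates each patient to a tolerated dose. In such a design some intolerance shows up as patients who stay in the trial on less drug than they were assigned. A table limited to discontinuation cannot show them. Two arms could have similar counts of "patients discontinuing the study due to AE" while differing in how many patients could not be kept on their assigned dose.

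This matters for interpretation because the primary comparison is of the assigned high dose with placebo. A reader of the results will want to know how often that dose was reduced or interrupted because of an adverse event, and the SAP names no table that answers this by arm.

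**Working it through.** The plan states no figure on this point, so there is nothing to reproduce. The check has two parts: whether another planned output recovers the information, and how large the gap could be.

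**1. Do other outputs recover it?**

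- *All-TEAE, relationship and ADR tables (SAP 17.1.1, 17.1.6).* These count the events, but nothing in their description separates events that led to a dose change from those that did not.
- *Intensity.* Protocol 13.1.2 grades intensity by disability and need for treatment, not by effect on dosing. An event that prompted a dose cut and then resolved untreated without disability fits the mild grade, so intensity is not a substitute.
- *Exposure (SAP 13).* Take two patients first dosed on Day 1 and last dosed on Day 168, one on full dose throughout and one reduced or interrupted along the way. Both have 168 − 1 + 1 = 168 days. The dose-level and capsule summary in protocol 15.2.3 would help separate them, but the SAP does not carry it over.
- *Non-compliance (SAP 14).* This is a listing of patients below 80%, with no link to adverse events and no comparison by arm. The SAP gives no compliance formula. Assuming capsules taken over capsules planned at two per day, the plan is 168 × 2 = 336 capsules, and 80% of that is 268.8. Giving one of the two daily doses for k days leaves 336 − k, which falls below 268.8 only if k exceeds 67.2. A step of a few days would not be listed. A move to a lower dose still given as one capsule twice daily would leave compliance unchanged.

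**2. How large could the gap be?**

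Within an arm, let d be the proportion of patients with an adverse event leading to discontinuation, and r the proportion whose events led only to reduction or interruption. The share of affected patients absent from the discontinuation table is

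share = r / (d + r).

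The documents give neither d nor r. The 25% attrition in the sample-size section is all-cause and does not supply d. Assumed ranges are d = 5–15% and r = 5–30%:

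| | r = 5% | r = 10% | r = 20% | r = 30% |
|---|---|---|---|---|
| d = 5% | 50% | 67% | 80% | 86% |
| d = 10% | 33% | 50% | 67% | 75% |
| d = 15% | 25% | 40% | 57% | 67% |

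In patients, with about 43 per group (protocol 9.1):

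- Lowest share: r = 5%, d = 15%. Dose change only 43 × 0.05 = 2.15; total affected 43 × 0.20 = 8.6; share 0.05/0.20 = 25%.
- Highest share: r = 30%, d = 5%. Dose change only 43 × 0.30 = 12.9; total affected 43 × 0.35 = 15.05; share 0.30/0.35 = 86%.

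The share exceeds one half only when r is greater than d.

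**The case against.** The strongest reply is that these events are not lost. The SAP tabulates all TEAEs by SOC/PT, intensity and relationship, and also serious TEAEs, ADRs and deaths. An event that led to a dose cut is counted in the general TEAE tables and, if related, in the ADR table. That is correct. A reader might infer that the SAP tabulates only events that end participation; it does not. The restriction to discontinuation applies only to summaries by action taken.

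A reader might also infer that most dose-limiting harm goes unseen. No document gives a rate to support that, and the table above shows it depends on r exceeding d. Nor is discontinuation strictly a last step: protocol 14 allows withdrawal for an adverse event the investigator judges severe enough, without a prior dose reduction. What tolerability information there is does not point to high rates. SAP 1 reports no signs of intolerance in emerging trial data, and protocol 7.1.4 reports no tolerability findings in the Parkinson's disease studies at up to 10 mg twice daily. The first is partial and the second is from another population, but neither supports assuming a large r.

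Two further points stand. The protocol's own between-group comparison (15.2.5) does not name dose modification, so the omission begins there. And SAP 17.1 refers the overview to templates that are not among the documents, while the columns of the TEAE listing are not stated. It can be said that no summary is named, not that the action taken is shown nowhere.

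None of this supplies the missing by-arm count, and the exposure discrepancy is not explained by the protocol's analysis section, since 15.2.3 promises what SAP 13 leaves out.

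**Conclusion.** The point holds as a reporting gap. As written, the SAP provides no named count, by arm, of patients whose dose was reduced or interrupted because of an adverse event, in a design that permits both and on an objective that includes tolerability. The events are counted but not labelled as dose-limiting. Separately, SAP 13 omits the dose-level and capsule summary in protocol 15.2.3 while SAP 3.3 declares no changes.

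The size is unknown. The 25% to 86% range rests entirely on assumed rates and describes one table, not the whole safety comparison. The conclusion also assumes that the action-taken field was built into the CRF as protocol 13.1.2 describes. The primary analysis and its error rate are not affected. The change is worth making because it is cheap and bears directly on a stated objective.

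**What to change.** In SAP 17.1.1 and 17.1.4 add, by arm and by SOC/PT, the number and percentage of patients with a TEAE leading to (a) dose reduction, (b) interruption, and (c) any study-drug change, meaning reduction, interruption or discontinuation. Derive all three from the action-taken field.

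In defining (c), state which discontinuation is meant. SAP 17.1.4 counts discontinuation of the patient, whereas protocol 15.2.5 ties adverse dropouts to discontinuation of study medication, and protocol 13.1.2 records the two separately.

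In SAP 13, restore the count of subjects at each dose level and the capsules taken, as protocol 15.2.3 states, or record the omission in SAP 3.3.

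The cost is a few additional safety tables and overview rows, using the action-taken field the protocol already requires. Dosing rules, alpha, power and sample size do not change. The tables should be specified before unblinding; added afterwards, they would be post hoc.

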17.1.5 SERIOUS ADVERSE EVENTS

Serious adverse events (SAEs) are those events recorded as “Serious” on the Adverse Events page of the eCRF. A summary of serious TEAEs by SOC and PT will be prepared.

17.1.6 ADVERSE DRUG REACTION (ADR)

All noxious and unintended responses to a medicinal product related to any dose should be considered as adverse drug reactions. ADR is a related event, so it is a TEAE that is related as defined in Section 17.1.3

A summary of ADR by SOC and PT will be prepared.

Any ADR during the study will be presented in a data listing.

17.1.7 SUMMARY OF NON-TEAEs

Not applicable. Non-TEAEs will be in the data listing.

17.2. DEATHS

Any deaths during the study will be presented in a summary table and a data listing.

17.3. LABORATORY EVALUATIONS

Results from the central laboratory will be included in the reporting of this study for hematology, clinical chemistry, urinalysis, thyroid function tests, virology, serum pregnancy test for post-pubertal females, HPA axis and prolactin. A list of laboratory assessments to be included in the outputs is included in the protocol.

Quantitative laboratory measurements reported as “< X”, i.e. below the lower limit of quantification (BLQ), or “> X”, i.e. above the upper limit of quantification (ULQ), will be converted to X for the purpose of quantitative summaries, but will be presented as recorded, i.e. as “< X” or “> X” in the listings.

Document:	\\ieedc-vnasc01\BIOSdata\Newron\Sarizotan\PXA76395\Biostatistics\Documentation\SAP		
Author:	[name]	Version Number:	V2
		Version Date:	[30March2020]
Template No:	CS_TP_BS016 – Revision 4	Reference:	CS_WI_BS005
Effective Date:	01Apr2016		

The following summaries (descriptive statistics for quantitative measurements and count and percentage for qualitative measurements except urinalysis) will be provided for laboratory parameter (i.e. hematology, clinical chemistry, urinalysis, HPA axis, Serum Pregnancy Test and prolactin).

- Actual and change from baseline by visit (for quantitative measurements).
- Shift from baseline to Week 24 and End of Study visits according to standard normal range criteria (for quantitative measurements and categorical measurements).
- Incidence table at Week 24 and End of Study visits according to clinically notable values (for quantitative measurements and categorical measurements).
- Listing of subjects' laboratory evaluations with flagging of abnormal values.

The descriptive statistics for actual measurement and change from baseline by treatment group will be performed at scheduled visits.

17.4. 12-LEAD ECG

ECG analysis related details can be found in ECG SAP.

17.5. VITAL SIGNS

The following vital signs measurements will be reported for this study:

- Systolic Blood Pressure (mmHg)
- Diastolic Blood Pressure (mmHg)
- Pulse (bpm)
- Respiratory Rate (breaths/min)
- Body Temperature (⁰C)

The following summaries will be provided for vital signs data:

- Actual values and change from baseline by visits and timepoints
- Incidence of clinically notable vital signs values at Day 1, Day 15, Week 24 and End of Study visits as defined in Appendix 3 of the SAP
- Listing of patients' vital signs

The descriptive statistics for actual measurement and change from baseline will be presented by treatment group and timepoints at scheduled visits.

Document:	\\ieedc-vnasc01\BIOSdata\Newron\Sarizotan\PXA76395\Biostatistics\Documentation\SAP		
Author:	[name]	Version Number:	V2
		Version Date:	[30March2020]
Template No:	CS_TP_BS016 – Revision 4	Reference:	CS_WI_BS005
Effective Date:	01Apr2016		

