The study medication will be administered as capsules of 2-mg, 5-mg or 10-mg dosage strength of sarizotan or matching placebo capsules. The capsules should be given orally; however, if necessary, they can be dissolved in an appropriate liquid and administered as a solution either orally or through an enteral feeding tube, e.g. gastrostomy tube (G-tube). Patients will receive 1 capsule *bid*, with combinations of active and placebo (double-blind period only) capsules being used to achieve the desired daily dose of sarizotan. Study medication with each different dosage (2-mg, 5-mg or 10-mg sarizotan, or placebo) will be provided in kits for dispensing to the patient for twice daily dosing over the period between scheduled visits. In the double-blind period, the study medication (sarizotan 2 mg, 5 mg or 10 mg, or placebo) administered to each patient will be determined according to a computer-generated randomization scheme. Drug supplies, randomization of patients to treatment (double-blind period only), and dispensing of appropriate medication kits (double-blind and open-label periods) will be managed by an Interactive Voice or Web Response System (IWRS).

Comparator – Dose and Mode of Administration:

In the initial 24-week double-blind period, patients randomized to the placebo group will be administered an equal number of matching placebo capsules (1 capsule *bid*) at each dose level.

Methodology:*Safety Outcomes – Secondary Objective*

Safety will be assessed by the following:

- Adverse events (AEs)
- Vital signs (systolic/diastolic blood pressure, pulse, body weight, body temperature, respiratory rate)
- Laboratory evaluations (blood chemistry, hematology, urinalysis, serum prolactin, and plasma ACTH and cortisol)
- Electrocardiogram (ECG) – 12-lead standard
- Physical examination
- Neurological examination
- Routine ophthalmology examination (including OCT, if feasible for the patient)
- Tanner Staging
- Suicidality assessment.

Primary Efficacy Outcome

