Two sarizotan *dose-range-finding studies* conducted in juvenile rats, an initial study ([ONP0106](#)) in which treatment started in 21-day old pups (corresponding to a 2-year old child), and a 2nd study ([ONP0113](#)) in 7-day old pups (corresponding to a newly born child), indicated the presence of effects on body weight, and relatively severe CNS signs in the 7-day old pups, thus limiting the *main study* (YG47PW) to be performed in 21-day old pups, at doses of 0, 12.5, 25 and 50 mg/kg/day. In this study, at the 50 mg/kg dose, a treatment-related death was observed, as well as CNS signs (underactive behavior, flat posture, piloerection, and splayed limbs); similar signs, but of a lower severity, were encountered in all dose groups (including 12.5 and 25 mg/kg), which resolved during the day. In addition, reduced ulnar growth (50 mg/kg), abnormalities in weight gain (50 mg/kg males, all groups females), oestrus irregularity (all groups), delay in reproductive maturity (50 mg/kg), abnormalities in motor activity (50 mg/kg) and during the functional operational battery (FOB) (all groups), and impairments in learning and memory (all groups) were noted. All of the above changes showed recovery, apart from the increase in motor activity. Despite treatment-related histopathological changes (large corpora lutea, vaginal dioestrus, mammary gland hypertrophy/hyperplasia, and adrenal gland zona glomerulosa hypertrophy) during treatment, there was no difference between sarizotan and placebo-treated animals during recovery. There was no evidence of an effect of any of the doses on mating behavior, pregnancy, conception and fertility indices, or the number of live embryos or litter size.

Amend. 1, 19Jan2016; Amend. 2, 18May2016; Amend. 3, 21Oct2016; Amend. 4, 03Mar2017; Amend. 5, 29Mar2017; Amend. 6, 13Apr2017; Amend. 7, 02Oct2017; Amend. 8, 02Nov2017; Amend. 9, 11Feb2018; Amend. 10, 29Nov2018; Amend. 13, 10Dec2019; Amendment 14, 17 March 2020, Clean, Final

The Functional Observational Battery (FOB) revealed an increase in vocalisation, particularly in females, in all treated groups during the in-hand observations, and an increase in the incidence of flattened posture, abnormal gait, tremors, urination and defecation, and a decrease in the levels of arousal and rearing during the 2-minute arena observation. All arena counts, except high urination and fecal counts, showed full recovery.

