15.2.5 Safety evaluations

All subjects who receive a dose of study medication will be included in the safety analyses. All adverse events will be listed and summarized by body system and preferred term. The incidence of AEs (%) and their relatedness to the study drug, as assessed by the Investigator, will be reported. Serious adverse events (SAEs) and events which are newly occurring or worsening after administration of the study medication (TEAEs) will be summarized. In addition, adverse events that result in death or discontinuation (ADOs) of the study medication will be listed separately.

Results for other safety parameters such as vital signs, laboratory parameters, ECGs, physical, neurological and ophthalmological examinations, and the suicidality assessment, will be listed and summarized accordingly. Changes from baseline in vital signs, ECG and laboratory values, and physical, neurological and ophthalmological examination findings will be summarized, with abnormal and clinically notable values/findings being identified. In the initial 24-week, double-blind, placebo-controlled period, a comparison will be made between the sarizotan and placebo groups in the proportion of subjects experiencing SAEs, ADOs, and TEAEs and any clinically significant abnormalities in other safety parameters. Where feasible, mean changes from baseline will be examined using a paired t-test. Safety data for the open-label extension period will be analyzed separately and will use the Week 24 evaluations from the double-blind period as the baseline assessments.

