Variable	Clinically Notable Values
Protein	Increase of 2 units
Glucose	Increase of 2 units

CLINICALLY NOTABLE VITAL SIGNS VALUES

Parameter	Unit	Decrease	Increase
Sitting/Supine SBP	mmHg	Value ≤ 90 and ≥ 20 decrease from Baseline.	Value ≥ 180 and ≥ 20 increase from Baseline
Sitting/Supine DBP	mmHg	Value ≤ 50 and ≥ 15 decrease from Baseline.	Value ≥ 105 and ≥ 15 increase from Baseline
Orthostatic Hypotension (based on standing SBP/DBP)	mmHg	Decrease in SBP/DBP from Supine to Standing position exceeding > 30mmHg	NA
Sitting pulse rate	bpm	Value ≤ 50 and ≥ 15 decrease from Baseline	Value ≥ 120 and ≥ 15 increase from Baseline
Weight	kg	≥ 7% decrease from Baseline.	≥ 7% increase from Baseline.
Respiration rates*	Breaths/minute	< 12	> 25
Temperature	°C	NA	Value ≥ 38.3 and ≥ 1.1 increase from Baseline.
Temperature	°F	NA	Value ≥ 101.0 and ≥ 2.0 increase from baseline

* For respiration rate values are relevant, not decrease/increase.

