APPENDIX 3. CLINICALLY NOTABLE VITAL SIGNS VALUES

Parameter	Unit	Decrease	Increase
Sitting/Supine SBP	mmHg	Value ≤ 90 and ≥ 20 decrease from Baseline.	Value ≥ 180 and ≥ 20 increase from Baseline
Sitting/Supine DBP	mmHg	Value ≤ 50 and ≥ 15 decrease from Baseline.	Value ≥ 105 and ≥ 15 increase from Baseline
Orthostatic Hypotension (based on standing SBP/DBP)	mmHg	Decrease in SBP/DBP from Supine to Standing position exceeding > 30 mmHg	NA
Sitting pulse rate	bpm	Value ≤ 50 and ≥ 15 decrease from Baseline	Value ≥ 120 and ≥ 15 increase from Baseline
Weight	kg	$\geq 7\%$ decrease from Baseline.	$\geq 7\%$ increase from Baseline.
Respiration rates*	Breaths/ minute	< 12	> 25
Temperature	$^{\circ}\text{C}$	NA	Value ≥ 38.3 and ≥ 1.1 increase from Baseline.
Temperature	$^{\circ}\text{F}$	NA	Value ≥ 101.0 and ≥ 2.0 increase from baseline

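### SAP 17.5 leaves body weight and height out of the vital signs summarized as change from baseline, although the protocol counts both as vital signs and the SAP declares no departure

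*SAP*

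**What the plan says.** **Protocol.** The safety outcomes in the Synopsis include "Vital signs (systolic/diastolic blood pressure, pulse, body weight, body temperature, respiratory rate" among their items. Section 12.1 gives a fuller definition of vital signs that adds height. Section 15.2.5 sets the analysis commitment: "Changes from baseline in vital signs, ECG and laboratory values, and physical, neurological and ophthalmological examination findings will be summarized". The visit lists in 11.4 and the text of 12.1.2 put weight at every clinic visit. Height is scheduled at Screening, Baseline and Weeks 8, 16 and 24 of the double-blind period.

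**SAP.** Section 17.5 begins "The following vital signs measurements will be reported for this study" and lists five measurements, with neither weight nor height. For the vital signs it covers, it says: "The descriptive statistics for actual measurement and change from baseline will be presented by treatment group and timepoints at scheduled visits". It also plans a categorical table: "Incidence of clinically notable vital signs values at Day 1, Day 15, Week 24 and End of Study visits as defined in Appendix 3". Appendix 3 has a weight row, a 7% decrease or increase from baseline, and no height row. The protocol's Appendix 2 has the same weight criterion ("≥ 7% decrease from Baseline" for losses). SAP 3.3, on changes from the protocol, reads none.

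**Background.** For the main juvenile rat study, protocol 7.1.2 reports "abnormalities in weight gain (50 mg/kg males, all groups females" and reduced ulnar growth at 50 mg/kg. It adds that these changes recovered, apart from motor activity.

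**The concern.** A programmer who follows the 17.5 list will produce change-from-baseline tables for five vital signs and none for weight or height. The protocol promised that summary, and nothing in the SAP records that it was dropped.

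What is lost is the most direct view of growth. The trial enrolls from 4 years and 10 kg, and protocol 7.3 states that sarizotan had not been given to pediatric patients before. In the extension every patient receives sarizotan (protocol 15.2), so only the 24-week double-blind period has a concurrent placebo group against which to read weight and height. For weight, a reader of the report would see counts above a threshold. For height, a reader would see nothing after baseline.

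**Working it through.** The plan states no figure on this point, so there is none to reproduce. The check sets the texts side by side and then asks how far the 7% category can stand in for a mean change.

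**Step 1: coverage by parameter in the double-blind SAP**
- Five listed vital signs: actual value and change from baseline by arm; notable-value incidence under Appendix 3.
- Weight: not listed, so no actual value or change from baseline by arm. Incidence of a 7% change is available through Appendix 3, at Day 1, Day 15, Week 24 and End of Study only. Weeks 8 and 16 are not in that table.
- Height: not listed, no Appendix 3 criterion, so no post-baseline summary.

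Against protocol 12.1 and 15.2.5, two measurements that should have a change-from-baseline summary have none, and SAP 3.3 does not say so.

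**Step 2: what the weight flag can see.** The loss needed for a flag is 0.07 × baseline weight:
- 10 kg: 0.70 kg
- 15 kg: 1.05 kg
- 18 kg: 1.26 kg
- 25 kg: 1.75 kg

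A child whose weight stays flat for 24 weeks has a change of 0% and appears in neither category. Slowed growth is therefore visible only indirectly, as fewer 7% gains than on placebo.

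**Step 3: sensitivity, for illustration.** All growth inputs here are assumptions; the documents give none. Take 24-week percent weight change as normal with a common SD, a mean gain on placebo and zero mean gain on active. Power at two-sided 0.05 serves only as a yardstick of the information each summary keeps. It is not a proposal to test.

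Worked case: SD 5, placebo mean 4%, active mean 0%, n = 43 per arm.
- Loss of at least 7%: placebo Φ((−7 − 4)/5) = Φ(−2.2) = 0.014; active Φ(−7/5) = Φ(−1.4) = 0.081.
- Gain of at least 7%: placebo 1 − Φ((7 − 4)/5) = 1 − Φ(0.6) = 0.274; active 1 − Φ(1.4) = 0.081.
- Power for two proportions, Φ{[|p₀ − p₁| − 1.96√(2p̄(1 − p̄)/n)] / √[(p₀(1 − p₀) + p₁(1 − p₁))/n]}: 31% for losses, 66% for gains.
- Power for means, Φ{4/(5√(2/43)) − 1.96} = Φ(3.71 − 1.96) = Φ(1.75) = 96%.

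Range over SD 3 to 7, placebo gain 2% to 6%, and 34 to 43 per arm (the protocol's completers and enrolled per group):
- loss category: 7% to 52%
- gain category: 13% to over 99%
- mean change: 22% to over 99%

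In every scenario the mean was at least as sensitive as either category.

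**The case against.** Several points on the other side are sound.

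- **Weight is not absent.** A reader might infer that growth is never compared between arms as a change from baseline. The documents do not support that for weight: 17.5 calls on Appendix 3 by name, and its weight row is defined as a change from baseline. This stands.
- **Height is not measured at every visit.** The Day 1, 2, 14 and 15 lists in protocol 11.4 include weight but not height. This stands; the gap for height concerns Weeks 8, 16 and 24.
- **No between-arm test of mean weight change was promised.** Protocol 15.2.5 promises summaries and, where feasible, paired t-tests, which are within-group. Its sarizotan-placebo comparison concerns proportions, and the weight incidence is of that kind. This stands. What is missing is the descriptive summary.
- **Normal growth triggers the 7% gain flag.** That alone is no defect, because the placebo group shares normal growth under either measure. The fair criticism is lower sensitivity.
- **The animal findings are qualified.** They recovered; reduced ulnar growth was seen only at 50 mg/kg, above the stated 25 mg/kg/day NOAEL; and protocol 7.1.2 says earlier human trials detected no growth effect. These points lower the prior concern. They do not replace looking: the weight-gain effect in females appeared in all dose groups, predicted safety margins at the NOAEL are one- to fivefold, and the earlier trials included no pediatric patients.
- **The SAP covers the double-blind phase only.** A separate open-label SAP is announced and was not available. Since all extension patients receive sarizotan, it cannot supply a placebo comparison.

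**Conclusion.** The point holds as a minor but genuine conflict between protocol and SAP. Weight and height are missing from the change-from-baseline summary that the protocol commits to, and the SAP declares no change. Weight is kept only as a 7% category, tabulated at four time points; height has no post-baseline summary.

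The textual finding needs no assumption. The statement that the category is a weaker measure of slowed growth rests partly on simple arithmetic (a child with no gain is not flagged) and partly on the assumed growth means and SDs above, so those power figures are illustrative. Nothing here bears on the primary analysis, alpha or sample size, and the documents do not show that sarizotan impairs growth in children. A reader might also conclude that the plan hides a growth effect. The text does not support that: the measurements are collected, and the weight flag remains.

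**What to change.** Add body weight (kg) and height (cm) to the list in SAP 17.5, with descriptive actual values and change from baseline by treatment group: weight at scheduled visits, height at Baseline and Weeks 8, 16 and 24. Present the same descriptively for the existing age groups, under 13 and 13 or older, with no inferential statistics in those subgroups, as SAP 7.5 requires. Keep the Appendix 3 weight incidence as it stands. Between-arm confidence intervals are not needed to meet the protocol and would go beyond the descriptive plan for vital signs.

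The cost is two added parameters in the list and the corresponding rows or tables in the outputs. No new data, visits or alpha are involved.
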